7.1.3.6 Bone Marrow Aspirate and Peripheral Blood for Minimal Residual Disease (MRD) Assessment

Minimal residual disease assessment will be performed by flow cytometry at Screening for every subject to detect a dominant clone in peripheral blood or bone marrow aspirate. MRD negativity will be assessed by flow cytometry both in the peripheral blood and the bone marrow aspirate collected at documented CR. Thereafter subjects should be followed with peripheral blood MRD analyses by flow cytometry every 12 weeks (±7 days) for the remaining first year; every 16 weeks during the second and third years; and every 24 weeks thereafter until PD. MRD-negative remission is defined as undetectable MRD at documented CR in subjects who were MRD positive at screening as assessed by flow cytometry in bone marrow (BM) aspirate and/or peripheral blood and a consecutive peripheral blood sample 12 weeks later.

If the MRD assessment is positive in bone marrow at CR, a repeat bone marrow aspirate is required 24 weeks later if the subject remains in CR to evaluate MRD status in the bone marrow.

If peripheral blood becomes positive for MRD, a bone marrow sample will not be necessary; however, equivocal cases should be discussed with the medical monitor to determine the need for repeat bone marrow testing.

MRD-positive relapse is defined as a detectable increase in disease after a MRD-negative remission, as assessed by flow cytometry of a peripheral blood or BM aspirate sample.

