10.2.3 Randomization Phase Secondary Endpoints

Efficacy:

- Complete response rate (CR) based on the best overall response per investigator assessment according to the Revised Response Criteria for Malignant Lymphoma (Cheson 2014).
- Overall response rate (ORR), defined as CR or PR per investigator assessment according to the Revised Response Criteria for Malignant Lymphoma (Cheson 2014).
- MRD-negative remission rate in subjects who achieve CR per investigator assessment. A MRD-negative remission is defined as undetectable MRD at documented CR in subjects who were MRD positive at screening as assessed by flow cytometry in bone marrow and/or peripheral blood, with requirement of confirmation of MRD negativity in the subsequent peripheral blood 12 weeks later. OS, defined as the time from randomization to death from any cause.
- DOR, defined for subjects who achieve an overall response as the time from the first occurrence of response (CR or PR) to disease progression or death, whichever occurs first.
- TTNT, defined as the duration from the date of randomization to the start date of any anti-lymphoma treatment subsequent to study treatment.

Safety:

- Frequency, severity, and relatedness of AEs
- Frequency, severity and management of TLS
- Frequency of AEs requiring discontinuation of study drug or dose reductions, or leading to death

Pharmacokinetics:

- Pharmacokinetics of ibrutinib at steady state
- Pharmacokinetics of venetoclax at steady state

Patient Reported Outcomes (PRO):

• Time to worsening in FACT-Lym subscale of the health-related quality of life questionnaire (FACT-Lym)

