- ^j CT and PET or PET/CT: A CT scan (with contrast unless contraindicated) of the neck, chest, abdomen, and pelvis and any other disease sites (eg, extremity) and a PET or PET/CT scan (CT should be of diagnostic quality) are required for the pretreatment tumor assessment within 28 days of the first dose. Thereafter, CT scans will be done for tumor assessments on Week 13 Day 1 (±7 days); every 12 weeks for the remainder of the 1st year; every 16 weeks during the 2nd and 3rd years; and every 24 weeks thereafter until PD. PET or PET/CT is mandatory to confirm a CR. For MRI refer to Section 7.1.3.2.
- ^k A total of up to 20 slides of fresh or the most recent dated FFPE archival tumor biopsy tissue will be required at study entry. An optional tumor biopsy should be collected at the time of disease progression if feasible.
- A unilateral bone marrow aspirate will be done at Screening or up to 28 days before the 1st administration of study drug for MRD testing. A 2nd bone marrow aspirate will be performed in all subjects who achieve a CR. Subsequent bone marrow aspirates will be obtained as needed (ie, if MRD in BM at CR was positive, and subject remains CR) to confirm MRD-negative CR.
- m Response assessments will be completed by the investigator using the Revised Response Criteria for Malignant Lymphoma (Cheson 2014).
- ⁿ Blood will be drawn for MRD assessments at baseline, at documented complete response and onwards every 12 weeks (±7 days) for the remainder of the 1st year; every 16 weeks during the 2nd and 3rd years; and every 24 weeks thereafter until PD.

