	To support ORR, duration of response (DOR) is defined for the responders (PR or CR) as time from the date of initial response (PR or CR, whichever occurs first) to the date of first documentation of PD or death, whichever occurs first, regardless of the use of subsequent anticancer therapy. Censoring convention is the same as for the PFS primary analysis.	
	For the US, additional censoring conventions as specified for the US primary PFS analysis in item 3) under Analysis Method will be implemented for duration of response.	
Minimal Residual Disease (MRD)- Negative Remission Rate	For CR subjects per investigator only: Proportion of subjects achieving an MRD- negative remission, which is defined as undetectable MRD (i.e. less than the lower limit of detection for the assay) at documented CR in MRD-evaluable subjects (i.e. subjects with positive MRD at baseline) as assessed by flow cytometry of bone marrow aspirate (BMA) and/or peripheral blood (PB)), with requirement of a confirmation of MRD- negativity in subsequent peripheral blood samples at least 12 weeks later. Only subjects with samples collected at both baseline and post-baseline are included in the	For CR subjects who were MRD-evaluable, the MRD-negative remission rate will be calculated and tested by Fisher's Exact test for BMA and PB separately.
	baseline and post-baseline are included in the denominator when calculating the MRD remission rate. MRD samples collected after the initiation of subsequent anticancer therapy will not be used for this analysis.	

Efficacy Endpoint	Definition	Analysis Method	
Overall	Time from the date of randomization to the	Primary Analysis:	
Survival (OS)	date of death due to any cause.	Similar to the primary PFS analysis, composite variable strategy (COVID-19 deaths are considered OS events) is implemented to address the intercurrent events of COVID-19 deaths. Subjects without an OS event will be censored at the date last known alive.	
		Analysis methods are the same as the primary PFS analysis.	
		Sensitivity/ Supplemental Analyses:	
		1) Unstratified log-rank test and unstratified Cox regression model to calculate HR and its 2-sided 95% CI.	
		2) Hypothetical strategy (Subjects who died due to COVID-19 are censored at one day prior to the death date) is implemented to address the intercurrent events of COVID-19 deaths	

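### MRD-negative remission is tested separately in marrow and blood, but the positive baseline that makes a subject evaluable is not tied to either compartment

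*SAP*

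**What the plan says.** SAP Section 4.2, Table 2, restricts the rate to subjects in CR per investigator. Its definition cell describes the eligible set as "MRD-evaluable subjects (i.e. subjects with positive MRD at baseline) as assessed by flow cytometry of bone marrow aspirate (BMA) and/or peripheral blood (PB"). The analysis cell then reads: "For CR subjects who were MRD-evaluable, the MRD-negative remission rate will be calculated and tested by Fisher's Exact test for BMA and PB separately". The denominator rule begins "Only subjects with samples collected at both baseline and post-baseline are included in the" denominator and concerns availability of samples, not their results. A remission also needs confirmation of "negativity in subsequent peripheral blood samples at least 12 weeks later", and this applies to both rates.

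The protocol does not supply the missing link:

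- Section 7.1.3.6 has every subject tested at screening "to detect a dominant clone in peripheral blood or bone marrow aspirate".
- Section 10.2.3 defines the endpoint "in subjects who were MRD positive at screening as assessed by flow cytometry in bone marrow and/or peripheral blood", with no matching by compartment.
- Section 10.5.1.2.3 describes a single rate. The split into a marrow rate and a blood rate appears only in the SAP.
- SAP Section 7 records the change to Fisher's exact test for this endpoint and adds no rule on evaluability.

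On sampling, Appendix A schedules the marrow aspirate at Screening and at CR. For blood it states: "Blood will be drawn for MRD assessments at baseline, at documented complete response and onwards every 12 weeks", with later draws at wider intervals.

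**The concern.** A positive baseline is normally required so that a later negative result shows that disease was cleared. That works for one subject-level rate. It stops working when the rate is split by compartment and the baseline requirement is not, because a subject can qualify through marrow and then be counted in blood, where there was nothing to clear.

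The blood rate would then mix true clearance with unchanged negatives. It would read too high, and the comparison between arms would depend partly on how many such subjects each arm happens to contain. The protocol also has an exploratory objective comparing MRD-negative remission in blood with that in marrow (Section 2.2.3), and never-positive subjects would blur that comparison.

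**Working it through.** The documents give no assumed MRD rate, sample size or power for this endpoint, so there is no stated figure to reproduce. The check is a trace through the rules, followed by an illustration.

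**Trace.** Take a complete responder who is marrow-positive and blood-negative at baseline.

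1. Evaluable? Yes: MRD was positive at baseline in one compartment.
2. In the blood denominator? Yes: blood is drawn at baseline and at CR.
3. Undetectable in blood at CR? Yes, if blood stays negative.
4. Confirmed at least 12 weeks later? Yes. The confirmation sample is also blood, so it repeats the baseline state.

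All written conditions are met with no change in blood.

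**Mirror case.** Take a subject positive only in blood. With negative marrow at baseline and at CR, this subject could count in the marrow rate although marrow was never positive. However, confirmation is in blood, which was positive at baseline, so blood must have turned negative. A real change is required, in the other compartment.

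**Size.** Let f be the share of evaluable complete responders who are marrow-positive and blood-negative at baseline and stay blood-negative. Let c be true blood clearance among blood-positive subjects. Both are assumptions.

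- Blood rate as written: f + (1 − f)c. Example: 0.20 + 0.80 × 0.50 = 0.60.
- Blood rate with matched evaluability: c.
- Difference between arms as written, equal f: (1 − f) × true difference. Example: 0.80 × 30 = 24 points.

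For scale only, 260 subjects randomized 1:1 give 130 per arm. The 55% and 20% CR rates in protocol Section 1.4.5 then give 130 × 0.55 ≈ 72 and 130 × 0.20 = 26 complete responders. This treats all of them as evaluable with complete samples, which is generous. Power is by exact enumeration of Fisher's test, two-sided 0.05, in favour of the combination. The matched groups are n(1 − f), rounded.

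| f | Rate as written, c = 50% | Rate as written, c = 70% | Difference as written, c = 70% vs 40% | Power as written, 70% vs 40% | Power matched, 70% vs 40% (n) |
|---|---|---|---|---|---|
| 0% | 50% | 70% | 30 points | 73% | 73% (72 vs 26) |
| 10% | 55% | 73% | 27 points | 65% | 70% (65 vs 23) |
| 20% | 60% | 76% | 24 points | 57% | 64% (58 vs 21) |
| 30% | 65% | 79% | 21 points | 50% | 57% (50 vs 18) |
| 40% | 70% | 82% | 18 points | 42% | 51% (43 vs 16) |

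In this scenario matching gains power despite the smaller groups. With clearance of 80% vs 50% the two rules are level at f = 10% (72% each), and matching is ahead at f = 20–40%.

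**Unequal f.**

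- Equal clearance of 50%, f = 10% in one arm and 30% in the other: 0.10 + 0.90 × 0.50 = 55% and 0.30 + 0.70 × 0.50 = 65%. A 10-point gap appears where there is none.
- Clearance of 70% vs 40%, f = 30% (combination) and 10% (control): 79% vs 46%, or 33 points, above the true 30.
- Same clearance, f = 10% and 30%: 73% vs 58%, or 15 points.

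**The case against.** The strongest reply is that the text leaves a rule unstated and does not lay down a wrong one. The bracket in the definition closes after the words on baseline positivity, and the phrase naming the two compartments follows outside it, ending in an unmatched bracket. That phrase may describe how negativity at CR is assessed. Testing the two compartments separately may also be meant to carry evaluability with it. This stands in part. A reader might infer that the SAP instructs the analyst to count never-positive subjects, and the documents do not support that. But under the bracket reading, baseline positivity names no compartment at all and the subject traced above still qualifies. The compartment-specific reading may be intended, but it is not written.

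Three further objections are sound:

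- **Mirror case.** A reader might infer that a blood-only-positive subject is credited in marrow in just the same way. The blood confirmation requirement rules that out.
- **Direction.** A reader might infer that the rule always shrinks the difference between arms. That needs equal f, and complete responders are a group selected after randomization, so equal f is not assured.
- **Purpose and range.** The documents do not say why a positive baseline is required, and they give no value for f. If f is zero, nothing changes.

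**Conclusion.** The point holds as a gap in specification. The written conditions let a subject who was never MRD-positive in blood count as a blood MRD-negative remission. At c = 50% the overstatement is f(1 − c), or 0 to 20 points for an assumed f of 0–40%, if such subjects stay blood-negative. A true difference of 30 points between arms would be reported as 30 down to 18 points with f equal in both arms. With unequal f the bias can go either way. The marrow rate has a weaker version of the problem.

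A reader might take this as a threat to the trial's error control. It is not: the MRD rate is a secondary endpoint that does not appear in the testing hierarchy of SAP Section 1.6.1 (PFS, then CR rate, time to next treatment, OS and ORR), and no figure stated in the documents changes. What is affected is the meaning of the blood rate and of its comparison between arms.

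**What to change.** Add to the MRD row of SAP Table 2:

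> The PB analysis includes CR subjects with a positive baseline PB MRD result. The BMA analysis includes CR subjects with a positive baseline BMA MRD result.

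Keep the either-compartment definition only for a combined subject-level rate, if one is reported, and label it as such. Correct the unbalanced bracket so that it is clear what the compartment phrase modifies.

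No new samples are needed: baseline marrow (Screening) and baseline blood (Week 1 Day 1) are already scheduled. The cost is a smaller denominator for each rate, in an analysis that SAP Section 7 already describes as small. SAP Section 1 says the plan is finalized before unblinding. Settling the rule by then avoids a later choice between two denominators with the results in view.

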1.4.4 Rationale for the Design of the Treatment Arms

The comparison between the ibrutinib and venetoclax combination with ibrutinib and placebo will evaluate the ability of the combined treatment to increase the complete response rate and progression-free survival (PFS) compared to ibrutinib monotherapy. Ibrutinib has shown a higher ORR and CR rate as monotherapy among treatments approved for relapsed or refractory MCL. (Campo 2015) and therefore serves as an appropriate control arm for this study.

1.4.5 Rationale for the PFS Assumption of 23 Months in the Ibrutinib and Venetoclax **Relapsed/Refractory Treatment Arm**

The primary endpoint in this study is PFS, with a null hypothesis of hazard ratio (HR) ≥ 1 for the ibrutinib and venetoclax group relative to ibrutinib and placebo group and an alternative hypothesis of HR of 0.61 corresponding to an improvement in median PFS from 14 months to 23 months. The PFS of 14 months for the ibrutinib + placebo group is based on results from previous studies with ibrutinib monotherapy in subjects with relapsed/refractory MCL (PCYC-1104-CA, MCL2001 and MCL3001), and the assumption of a PFS of 23 months for the ibrutinib and venetoclax group is based on the 24-month PFS rate estimated from subjects who achieved a CR in these studies.

In the pooled analysis of ibrutinib studies PCYC-1104-CA, MCL2001 and MCL3001, the ORR and CR rate were 65.7% and 20.0%, respectively. Importantly, the estimated 24-month PFS was 70% in the subjects who achieved a CR, compared to 19% in subjects who failed to achieve a CR (Rule 2016). In the venetoclax phase I trial, the CR rate in subjects with MCL was 21% (Gerecitano 2015), and no subjects with CR had experienced relapse. Therefore, based on these studies, subjects with a CR are likely to have better PFS. In addition, based on the preliminary efficacy results of the AIM study (Tam 2016, Tam 2017) for ibrutinib and venetoclax treatment, if the CR rate in the 1143 trial exceeds 55%, then under the exponential distribution assumption for PFS, the median PFS with the combination is predicted to be ≥ 23 months.

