2.2.2 Secondary Objectives

- To evaluate whether the combination of ibrutinib and venetoclax will increase the CR rate, the overall response rate (ORR), the minimal residual disease (MRD) negative remission rate in subjects who were MRD positive at screening and achieve CR, OS, DOR, and time-to-next treatment (TTNT) compared to ibrutinib and placebo.
- To evaluate the frequency, severity, and relatedness of AEs; frequency, severity and management of TLS; AEs requiring dose reductions and/or discontinuation of study drug, or leading to death.
- To determine the PK of ibrutinib and venetoclax.
- To evaluate whether the combination of ibrutinib and venetoclax will improve quality of life using a Health-related quality of life questionnaire (FACT-Lym) compared to ibrutinib and placebo.

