10.5.1.2.3 Minimal Residual Disease-Negative Remission Rate

The MRD-negative remission rate in subjects who were MRD positive at screening and achieve a CR will be calculated. The analysis methods of MRD-negative remission rate will be the same as those described in Section 10.5.1.2.1.

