7 CHANGES IN THE PROTOCOL-PLANNED ANALYSES

- 1. In alignment with the FDA guidance (Statistical Considerations for Clinical Trials During the COVID-19 Public Health Emergency, June 2020), in order to mitigate the potential impact on key efficacy endpoints due to COVID-19, the follow-up will be extended to accrue more events as described in Section 1.5.1 and Section 1.5.2 over the originally planned event numbers (134 events for PFS and 155 events for OS).
- 2. Change superiority boundary for the interim OS analysis from O'Brien Fleming boundary to Haybittle-Peto boundary.
- 3. Specify secondary and exploratory endpoints to be included in the CSR.
- 4. IRC will be implemented to do the overall disease assessment based on Cheson 2014 (Lugano Classification Criteria). A sensitivity analysis will be conducted for PFS using the IRC assessment.
- 5. Since only 9 subjects in total were randomized to the stratum of ECOG performance status of 2, stratification by the three randomization stratification factors will lead to empty or very small strata. Therefore, all stratified tests/analyses will only be based on two randomization stratification factors per IRT: prior lines of therapy (1-2 vs ≥ 3) and TLS risk category (low risk vs. increased risk).
- 6. The CR rate and ORR will be compared by rate ratio between the two treatment arms using CMH chi-square test stratified by the two randomization stratification factors instead of by the difference in proportion between the two treatment arms.
- 7. The MRD-negative remission rate for CR subjects evaluable for MRD will be compared by Fisher's Exact test due to the small sample size.

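### The MRD-negative remission p-value compares only subjects who reached CR, so it is not a randomized comparison, and no comparison over all randomized subjects is planned beside it

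*SAP*

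**What the plan says.** The protocol conditions this endpoint on CR throughout. Section 2.2.2 asks whether the combination will increase, among other things, "the minimal residual disease (MRD) negative remission rate in subjects who were MRD positive at screening and achieve CR". Section 10.2.3 lists the "MRD-negative remission rate in subjects who achieve CR per investigator assessment", and Section 10.5.1.2.3 repeats the restriction: "The MRD-negative remission rate in subjects who were MRD positive at screening and achieve a CR will be calculated". The protocol's method was the stratified CMH test used for CR rate.

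The SAP keeps the restriction and changes the test. Table 2 in Section 4.2 limits the analysis to investigator-assessed CR subjects who were MRD-positive at baseline: "For CR subjects who were MRD-evaluable, the MRD-negative remission rate will be calculated and tested by" Fisher's exact test. It adds that only subjects with samples at both "baseline and post-baseline are included in the denominator when calculating the MRD remission rate". Section 7, item 7 records the change: "The MRD-negative remission rate for CR subjects evaluable for MRD will be compared by Fisher's Exact test due to the small sample size".

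Neither document plans an MRD comparison over all randomized subjects. The exploratory MRD objectives in protocol Section 2.2.3 ask other questions (prognosis, MRD relapse, agreement between compartments and assays). SAP Section 1 places exploratory biomarker analyses outside its scope. MRD is not in the testing hierarchy of SAP Section 1.6.1.

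**The concern.** Randomization balances the arms at baseline. It does not balance the subsets that later reach CR and supply a sample. CR is itself tested as a treatment effect, first among the key secondary endpoints. Protocol Section 1.4.5 expects it to differ: in the pooled ibrutinib studies "the ORR and CR rate were 65.7% and 20.0%, respectively", and the planning condition for the combination is phrased as "if the CR rate in the 1143 trial exceeds 55" per cent. If venetoclax brings additional subjects into CR, the combination's CR group contains people with no counterpart in the placebo CR group.

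A within-CR difference then mixes two things: a change in depth of response, and a change in who is counted. At stake is how the MRD result is read. The secondary objective is worded as a treatment effect, and nothing in the SAP marks the p-value as descriptive. For its other responder-only measures, duration of CR and DOR, Table 2 gives Kaplan-Meier estimates by arm without a test.

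**Working it through.** **The plan's own figure.** The documents give no sample size, power, significance level or sidedness for this comparison, so there is none to reproduce.

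**Inputs from the documents.** 260 subjects randomized 1:1, so 130 per arm (protocol Section 10.3). CR 20% versus 55% (Section 1.4.5). If everyone is evaluable, the test sets 130 × 0.20 = 26 against 130 × 0.55 = 71.5, about 72 subjects.

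**Assumed inputs.** No control within-CR rate is given, so it is varied. For the combination, the AIM study suggests 67/71 = 94% (Section 1.4.7, if the 67% with MRD clearance lie within the 71% with CR). Other readings run from 100% (Section 1.4.2, all CR subjects cleared) down to 10/14 = 71% (Section 1.4, if four unconfirmed CRs are counted as not cleared). These are small samples without this trial's 12-week confirmation.

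**Method.** 20,000 simulated trials per scenario. CR is binomial, MRD-negativity is binomial within CR, and Fisher's test is two-sided at 0.05 (an assumption). The last column halves the number of evaluable CR subjects.

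| Within-CR rate, control / combination | MRD-negative CR over all randomized | Fisher significant, all CR evaluable | Fisher significant, half evaluable |
|---|---|---|---|
| 60% / 94% | 12% vs 51.7% | 96% for combination | 74% |
| 80% / 94% | 16% vs 51.7% | 46% for combination | 24% |
| 90% / 94% | 18% vs 51.7% | 9% for combination | 5% |
| 94% / 94% | 18.8% vs 51.7% | 2% for combination | 1% |
| 80% / 92.7% | 16% vs 51% | 37% for combination | 19% |
| 80% / 71% | 16% vs 39% | 10% against combination | 5% |

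The third column of figures is the one to treat as upper-end. The second is the within-CR rate times the CR rate, for example 0.20 × 0.94 = 18.8% and 0.55 × 0.94 = 51.7%.

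**Selection alone.** The 80% / 92.7% row assumes no change in depth among subjects who would reach CR on either arm (80% on both), and 100% MRD-negativity among those who reach CR only on the combination: (0.20 × 0.80 + 0.35 × 1.00) / 0.55 = 92.7%.

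**What an observed difference can mean.** Assume nobody reaches CR on placebo only. With 94% observed on the combination, the rate among subjects who would reach CR on either arm lies between (0.55 × 0.94 − 0.35) / 0.20 = 83.5% and 100%. Observed rates of 80% versus 94% then fit a depth effect of +3.5 to +20 points. Rates of 90% versus 94% fit −6.5 to +10 points. The within-CR comparison does not separate these.

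**The case against.** The strongest reply is that the SAP does what the protocol asks. The restriction to CR is in the objective, the endpoint and the analysis section. Only the test changed, and the change is documented with a reason. When within-CR rates are 94% in both arms, a non-significant result correctly answers the question as worded. This stands: a reader might infer that the SAP departs from the protocol's endpoint, and it does not.

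The illustrations also use two yardsticks. The 94% / 94% row is judged against the rate over all randomized subjects, and the 80% / 92.7% row against subjects who would reach CR on either arm. Neither is the stated endpoint. In the second case the combination does raise MRD-negative CR over all randomized subjects, so the direction of the test is right on that measure.

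The percentages are upper-end as well. The SAP cites a small sample as its reason for using Fisher's test, so far fewer than 98 subjects may be evaluable. The documents do not say how many. One compartment was simulated where the SAP plans two.

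A reader might further infer that the test is likely to come out significantly against the combination. That needs combination within-CR rates lower than most of the quoted AIM data suggest. It reaches 10% only at 80% / 71% with everyone evaluable.

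What survives is the structural point: following the protocol does not make a comparison of post-randomization subsets a randomized one.

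**Conclusion.** The point holds as a matter of interpretation. The planned p-value compares groups selected by CR and by sample availability, both arising after randomization, with CR expected to differ by arm. By itself it cannot show whether the combination increases MRD-negative remission, and no planned analysis fills that gap.

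The size of the distortion cannot be fixed from the documents. It depends on within-CR rates, the number evaluable, and the overlap between subjects reaching CR on each arm. The table shows the range under stated assumptions and is not a forecast.

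Impact is limited. MRD is outside the hierarchy in SAP Section 1.6.1, so a reader who infers a threat to the trial's type I error or to a confirmatory claim would be mistaken. CR rate is already compared over all randomized subjects. The within-CR rate is a legitimate description and should stay. This is an inexpensive improvement to consider, not a defect in the primary analysis.

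**What to change.** Add a row to SAP Table 2: the proportion with confirmed MRD-negative CR by arm, among all randomized subjects who were MRD-positive at baseline in the compartment analysed, for marrow and blood separately. Use all ITT subjects as the denominator in a sensitivity analysis. Test it with the stratified CMH method planned for CR rate.

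Count no CR as not MRD-negative. Count a CR with a missing MRD or confirmatory sample as not MRD-negative too, and show the number of such subjects by arm. State this as a new rule: the SAP's existing non-responder rule covers only subjects with no post-baseline disease assessment.

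Keep the protocol-defined rate among CR subjects, by arm with confidence intervals. Label any Fisher p-value for it as nominal and descriptive, not as a randomized treatment comparison. List the change in SAP Section 7, as protocol Section 10 allows, before unblinding.

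No new data are needed. Baseline MRD and MRD at CR are already scheduled (protocol Section 7.1.3.6), and marrow taken only at CR (Section 8.2.2) is enough.

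The cost is interpretive. The added measure contains the CR difference and overlaps with the CR-rate test: with equal depth (60% / 60%) and CR 20% versus 55%, it favours the combination in about 98% of trials. It is also less sensitive to depth alone. With CR 20% in both arms and depth 60% versus 90%, it detects the difference in about 22% (Fisher) to 27% (stratified CMH) of trials, against 66% for the within-CR test. It should therefore be labelled MRD-negative CR, not depth of response, and read beside the CR rate and the within-CR rate.
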